## 12.0 ADVERSE EVENT REPORTING

### 12.1 Definitions

**12.1.1 Adverse Event Definition** - An **adverse event** (AE) is any untoward medical occurrence in a patient administered a pharmaceutical product, which does not necessarily have a causal relationship with the treatment. An adverse event can be any unfavorable and unintended sign (eg, including an abnormal laboratory finding), symptom, or disease temporally associated with the use of the drug, whether or not it is considered to be drug related. This includes any newly occurring event or previous condition that has increased in severity or frequency since the administration of drug.

**12.1.2 Serious Adverse Event Definition** - A **serious adverse event** (SAE) is any adverse event, occurring at any dose and regardless of causality that:

- Results in **death**.
- Is **life-threatening**. Life-threatening means that the patient was at immediate risk of death from the reaction as it occurred, i.e., it does not include a reaction which hypothetically might have caused death had it occurred in a more severe form.
- Requires inpatient **hospitalization or prolongation of existing hospitalization**. Hospitalization admissions and/or surgical operations scheduled to occur during the study period, but planned prior to study entry are not considered AEs if the illness or disease existed before the patient was enrolled in the trial, provided that it did not deteriorate in an unexpected manner during the trial (eg, surgery performed earlier than planned).
- Results in **persistent or significant disability/incapacity**. Disability is defined as a substantial disruption of a persons' ability to conduct normal life functions.
- Is a congenital anomaly/birth defect.
- Is an **important medical event**. An important medical event is an event that may not result in death, be life-threatening, or require hospitalization but may be considered an SAE when, based upon appropriate medical judgment, it may jeopardize the patient or subject and may require medical or surgical intervention to prevent one of the outcomes listed in the definitions for SAEs. Examples of such medical events include allergic bronchospasm requiring intensive treatment in an emergency room or at home, blood dyscrasias or convulsions that do not result in inpatient hospitalization, or the development of drug dependency or drug abuse.

Clarification should be made between the terms “serious” and “severe” since they ARE NOT synonymous. The term “severe” is often used to describe the intensity (severity) of a specific event (as in mild, moderate, or severe myocardial infarction); the event itself, however, may be of relatively minor medical significance (such as a severe headache). This is NOT the same as “serious,” which is based on patient/event outcome or action criteria described above and are usually associated with events that pose a threat to a patient’s life or functioning. A severe adverse event does not necessarily need to be considered serious. For example, persistent nausea of several hours duration may be considered severe nausea but not an SAE. On the other hand, a stroke resulting in only a minor degree of disability may be considered mild, but would be defined as an SAE based on the above noted criteria. Seriousness (not severity) serves as a guide for defining regulatory reporting obligations.

## 12.2 Procedures for AE and SAE Reporting

All serious adverse events (SAEs) will be assessed in a timely fashion and, if deemed reportable, SAE reports will be forwarded to its institutional IRB per IRB reporting requirements (e.g., Hopkins events get reported to Hopkins IRB and notify Emory PIs).

Assessing Causality:

Investigators are required to assess whether there is a reasonable possibility that dose escalated RT caused or contributed to an adverse event. The following general guidance may be used.

**Yes:** if the temporal relationship of the clinical event to dose-escalated RT makes a causal relationship possible, and other drugs, therapeutic interventions or underlying conditions do not provide a sufficient explanation for the observed event.

**No:** if the temporal relationship of the clinical event to dose-escalated RT makes a causal relationship unlikely, or other drugs, therapeutic interventions or underlying conditions provide a sufficient explanation for the observed event.

### **12.3 Attribution**

The clinical Principal Investigator (PI) at each site or his designee will document his opinion and any supporting laboratory and clinical information of the potential attribution of the study treatment to any grade 3 or greater toxicity based on the following guidelines:

#### **12.3.1 Unrelated**

This category applies to those toxicities that are clearly and incontrovertibly due to extraneous causes (disease, environment, etc.)

#### **12.3.2 Unlikely (*must have any two criteria*)**

In general, this category can be considered applicable to those toxicities that are judged to be unrelated to the test treatment. A toxicity may be considered unlikely if or when:

1. It does not follow a reasonable temporal sequence from administration of the test treatment;
2. It could readily have been produced by the subject's clinical state, environmental or toxic factors, or other modes of therapy administered to the subject;
3. It does not follow a known pattern of response to the test treatment;
4. It does not reappear or worsen when the test treatment is re-administered.

#### **12.3.3 Possible (*must have any two criteria*)**

This category applies to those toxicities for which a connection with the test treatment administration appears unlikely but cannot be ruled out with certainty. A toxicity may be considered possibly related if and when:

1. It follows a reasonable temporal sequence from administration of the test treatment;
2. It could not readily have been produced by the subject's clinical state, environmental or toxic factors, or other modes of therapy administered to the subject;
3. It does follow a known pattern of response to the test treatment.

#### **12.3.4 Probable (*must have any two criteria*)**

This category applies to those toxicities that are felt with a high degree of certainty to be related to the test treatment. A toxicity may be considered probably related if and when:

1. It follows a reasonable temporal sequence from administration of the test treatment;

2. It could not reasonably be explained by the known characteristics of the subject's clinical state, environmental or toxic factors, or other modes of therapy administered to the subject;
3. It disappears or decreases on cessation or reduction in test treatment. There are important exceptions when a toxicity does not disappear upon discontinuation of the test treatment, yet treatment-relatedness clearly exists (e.g. bone marrow depression, fixed drug eruptions, tardive dyskinesia);
4. It follows a known pattern of response to the test treatment.

#### **12.3.5 Definite (*must have all four criteria*)**

This category applies to those toxicities that are felt to be incontrovertibly related to the test treatment. A toxicity may be considered definitely related if and when:

1. It follows a reasonable temporal sequence from administration of the test treatment;
2. It could not reasonably be explained by the known characteristics of the subject's clinical state, environmental or toxic factors, or other modes of therapy administered to the subject;
3. It disappears or decreases on cessation or reduction in dose with re-exposure to drug. (Note: this is not to be construed as requiring re-exposure of the subject, however, a category of definitely related can only be used when a recurrence is observed.)
4. It follows a known pattern of response to the test treatment.

The Emory IRB, Johns Hopkins University IRB and University of Miami IRB will be notified of the event happened at each site promptly per each IRB requirements.

**Intensity** for each adverse event, including any lab abnormality, will be determined by using the NCI CTCAE, version 4.0, as a guideline.

#### **12.4 Monitoring of Adverse Events and Period of Observation**

Adverse events, both serious and non-serious, and deaths that occur during the subject's study participation will be recorded in the source documents. All SAEs should be monitored until they are resolved or are clearly determined to be due to a patient's stable or chronic condition or intercurrent illness(es).

### **13.0 DATA AND SAFETY MONITORING PLAN (DSMP)**

#### **13.1 Good Clinical Practice**

The study will be conducted in accordance with the International Conference on Harmonisation (ICH) for Good Clinical Practice (GCP) and the appropriate regulatory requirement(s). The investigator will be thoroughly familiar with the appropriate use of the drug as described in the protocol and Investigator's Brochure. Essential clinical documents will be maintained to demonstrate the validity of the study and the integrity of the data collected. Master files should be established at the beginning of the study, maintained for the duration of the study and retained according to the appropriate regulations.

#### **13.2 Winship Cancer Institute Data Safety Monitoring Committee:**

The study will also be followed by the Winship Cancer Institute Data Safety Monitoring Committee to allow for local review and confirmation of proper study execution and safety measures.

**13.2.1** Patient safety, study efficacy and compliance will be reviewed at the Neuro-oncology Working Group meeting. The Data and Safety Monitoring Committee (DSMC) of the

Winship Cancer Institute will also oversee the conduct of this study (annually or semi-annually – depending on the risk level assigned to the protocol by the Winship Cancer Institute Clinical and Translational Research Committee). The DSMC will review pertinent aspects of study conduct including patient safety, compliance with protocol, data collection and efficacy. The committee will review the charts of 10% of patients enrolled to the study and two of the first 5 patients entered to the study. The Committee reserves the right to conduct additional audits if necessary. The clinical Principal Investigator (PI) at each site or his designee is responsible for notifying the DSMC about the accrual of patients when the first 5 have been entered to the study. The PI or designee will also notify the DSMC of study status within 2 months before the next scheduled review is due.

### **13.2.2 Procedures to assure data integrity and protocol adherence**

- 13.2.2.1** Imaging and clinical data will be analyzed in a quarterly meeting of investigators, clinical research coordinators and regulatory personnel.
- 13.2.2.2** Adverse event reporting will utilize NCI Common Terminology Criteria for Adverse Events (CTCAE) version 4.0 and is detailed in section 12.0 above.
- 13.2.2.3** Study Team Oversight: The study progress in terms of enrollment, activity of current patients under active treatment, observed toxicities will be reviewed in the monthly Emory Neuro-oncology Working Group. Here there will be random and selected case report form and chart review. Special and problematic items requiring additional attention will be addressed in separate sessions of the Neuro-oncology Working Group occurring up to weekly including selected study investigators, clinical research coordinators and regulatory personnel.
- 13.2.2.4** Training of investigators, clinical research coordinators and regulatory personnel at all sites will be performed by one of the principal investigators utilizing the written protocol and a summary of pertinent treatment activities. Completion of the training of investigators, clinical research coordinators and regulatory personnel will be documented on a study training log.
- 13.2.2.5** External Site Management: Enrollment will occur at Johns Hopkins University and University of Miami
  - Monitoring of Study Activity: Monitoring of study activity will occur by monthly review of enrollment activity of current patients under active treatment, observed toxicities by the investigator, clinical research coordinator and regulatory personnel at Johns Hopkins and University of Miami. The results of this review will be summarized and shared and logged monthly in written form (and verbal form when needed) with the Emory investigators.
  - Investigator Communication: Verbal investigator communication among three sites will occur and be logged quarterly to discuss the content mentioned above.
  - Reporting of Adverse Events Occurring at Johns Hopkins and University of Miami: The criteria and methods of collecting adverse event data outlined in section 12.0 will apply at Johns Hopkins and U of Miami also.
    - Each site Principal Investigators (PI) are responsible for review and assessment of all adverse events at their site as specified in the protocol. AEs, SAEs (initial and follow ups), and UPs will be reported to the each site IRB as per protocol requirements

including reporting SAEs and UPs within 24 hours of the participating site becoming aware of the event.

- Johns Hopkins and University of Miami sites are also responsible for the following:
  - Report events, as applicable, to their IRB.
  - Submit all acknowledgements of reports submitted promptly to their IRB to the Winship multisite coordinator or Emory PIs.
  - Resolve all queries related to the SAE report in a timely manner.
  - Maintain copies of each event reported in the subject's study records.
  - Enter AEs into Oncore® in a timely manner.
  - Enter SAEs and UPs into Oncore® or equivalent (depending on the institution) in the SAE category, in a timely manner.
- Winship multisite coordinator will inform all three sites of adverse events that require expedited reporting to local IRBs.
- Emory Lead investigator will review SAE data summary reports on a regular basis, at least annually
- Emory Lead investigator will submit SAE data summary reports to the Data Safety Monitoring Committee for review as per their guidelines.

### **13.3 On-site Audits**

Regulatory authorities and the IRB may request access to all source documents, data capture records, and other study documentation for on-site audit or inspection. Direct access to these documents must be guaranteed by the investigator, who must provide support given reasonable notice at all times for these activities.

The following applies for monitoring of Sub-sites:

At the study initiation, the PI, regulatory specialist, and research coordinators will perform a site initiation teleconference. During this teleconference, the Emory team will review the study, enrollment, reporting, and regulatory compliance. The participating site will have internal monitoring meetings. These meetings will include the investigators, the clinical research coordinator and the regulatory affairs coordinator and will meet at least on a monthly basis to review and discuss study data to ensure subject safety. The research coordinators will maintain one spread sheet which will summarize all the patient data for patients actively being treated on the trial as well as a roadmap detailing pending tests/treatments for each individual patient. The spread sheet will be shared with the Emory PIs. Teleconferences will be conducted monthly among the PIs and the research team with the participating sites. The purpose of the meetings is to discuss the enrollment, regulatory updates, monitor toxicities, and evaluate the progress of the trial. The minutes from the teleconference will be maintained in the regulatory binder for the study. In addition, electronic copies will be sent via email to the PIs at each site. Chart reviews will be performed on selected cases from the participating site to confirm that the data collection is accurate.

Winship's Multisite Coordinator will perform remote quarterly monitoring of participating sites' data and will perform an annual on-site monitoring visit as necessary per site enrollment. Monthly

reviews of data in OnCore will be conducted to ensure compliance or identify discrepancies

## 14.0 STATISTICAL CONSIDERATIONS AND METHODOLOGY

### 14.1 Primary Objectives

14.1.1 To determine the feasibility of using sMRI to guide dose-escalated RT for newly-diagnosed GBMs. Feasibility of this approach will be determined by whether treatment volumes based on sMRI can be co-registered with clinical images and transferred into the radiation treatment execution platform in a seamless manner, so that sMRI information can be efficiently applied to the patient treatment.

14.1.2 To determine the safety of using sMRI to guide dose-escalated RT for newly-diagnosed GBMs. The safety of this approach will be confirmed by assessing toxicity potentially attributable to the dose-escalated RT. Toxicity will be determined by CTCAE v4.0 criteria. If > 6 of 30 patients (> 20% of subjects) experience a grade 3 or greater toxicity by 6 months after completion of RT/TMZ that is ruled as at least possibly attributable to the dose-escalated RT, then the safety of this treatment approach will be questioned and require further review by the study team. Interim analyses with stopping rules are described later in this Section.

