## **4.0 PATIENT SAFETY**

- 4.1 Risks associated with dose-escalated RT (research-related).** The risks of dose-escalated RT are expected to be similar to the risks of standard dose RT for newly-diagnosed GBMs although the incidence may be slightly increased. Incidence of serious toxicities will be carefully monitored in treated patients and is a primary objective of this study. Potential toxicities are listed below:

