**14.4 Adverse event stopping rule:** Safety assessments will be performed throughout treatment, at two week intervals during RT and prior to each odd number adjuvant TMZ cycle following completion of RT. Toxicity will be carefully assessed using CTCAE v4.03 criteria, and the rate of radiation necrosis development will be determined. While we expect this regimen to be tolerated based on the previous experience reported by Tsien et al. [9], we will still employ an interim safety analysis with a special stopping rule if neurotoxicity is greater than expected. Because the expected incidence of late grade 3+ neurotoxicity with standard-of-care chemoradiation is ~5%, or 2 of 30 patients in our planned cohort, we will employ the following interim analysis and stopping rule after 10 subjects have completed treatment and have been followed for 6 months after completion of chemoradiation: if more than 2 subjects (out of 10) develop CTCAE v4.03 grade III or greater neurotoxicity (> 20% incidence) judged to be at least possibly due to RT by 6 months from completion of RT/TMZ, study accrual will halt and await assessment of toxicities by the DSMC to review attribution of toxicities before a decision will be made about either permanent closure or re-opening with continuation/completion of study accrual.

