**14.5 Statistical analysis for survival endpoints:** The primary objectives are to determine the feasibility of this escalated protocol and the safety of increased doses in patients with GBM. We anticipate that 30 patients will provide us sufficient data to make these conclusions. Since survival analyses are exploratory objectives of this study, these endpoints are not used to determine accrual numbers for this study. The PFS of patients in this protocol will be compared with historical controls, and that data will be used to estimate the effect size for future power analyses. With a planned accrual of 30 subjects, the following power to detect potential improvements in 1 year PFS is as follows: 1-year PFS rate is expected to be 30-35% based on historical controls [44-46]. Our study will have 82% power to detect an improvement to a rate of 60% at  $\alpha=0.05$  using a two-sided test. Cox's proportional hazard regression model will be applied to model 1-year PFS outcome to test whether subjects treated with escalated RT doses guided by the sMRI demonstrate significantly higher PFS as compared to historical controls receiving standard treatment, controlling for other potential risk factors. Of note, calculations to determine the power to detect a certain PFS effect size based the number of patients we needed to determine feasibility and safety were presented above. However, this study was not actually powered based on PFS improvement.

**14.6 Statistical analysis of sMRI scans:** This study is mainly using pre-RT sMRI parameters to help define a region at high risk for recurrence that can be treated with higher doses of RT. Exploratory objectives will involve examining changes in absolute metabolite levels and metabolic ratios during RT that may be useful for adaptive radiation therapy (changing dose plan during early phase of RT). sMRI data will be evaluated both on a patient-wise basis and on a voxel-wise basis with utilization of deformable registration technique, as needed, to achieve good matching of maps across serially acquired scans.

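### The safety threshold of more than 6 in 30 is a review trigger with no interval or error rates behind it; staying at or below it does not confirm safety, so the safety conclusion should rest on an exact confidence interval.

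*Combined protocol and SAP*

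**What the plan says.** Section 2.1 lists safety as one of two primary objectives. Section 14.1.2 states how it will be judged: "The safety of this approach will be confirmed by assessing toxicity potentially attributable to the dose-escalated RT". The criterion is a count over 30 patients. It is crossed when more than 6 have an event of grade 3 or worse within 6 months of finishing chemoradiation, provided the link to the escalated dose is judged possible or stronger. The stated consequence of crossing it is: "then the safety of this treatment approach will be questioned and require further review by the study team". The section does not say what may be concluded from 6 or fewer events.

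Section 14.4 adds one interim look, after 10 patients have been followed for 6 months: "we will still employ an interim safety analysis with a special stopping rule if neurotoxicity is greater than expected". More than 2 of 10 with grade 3 or higher neurotoxicity, at least possibly due to radiotherapy, halts accrual until the monitoring committee has reviewed attribution. The benchmark for this look is given as follows: "Because the expected incidence of late grade 3+ neurotoxicity with standard-of-care chemoradiation is ~5%, or 2 of 30 patients in our planned cohort".

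On sample size for the primary objectives, section 14.5 says only: "We anticipate that 30 patients will provide us sufficient data to make these conclusions". For 1-year progression-free survival, which did not determine the sample size, the same section gives a significance level, an alternative and a power. Neither safety rule has an unacceptable rate, error rate, confidence interval or operating characteristic.

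**The concern.** A count that triggers review and a result that confirms safety are different things. The plan announces confirmation and offers only the trigger, so the natural reading is that 6 or fewer events meets the objective. If that is not intended, a primary objective has no stated basis for a positive conclusion.

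Section 2.0 says safety has to be shown before the approach is adopted more widely. With 30 patients, a count just under the trigger is compatible with a true rate well above 20%. A report that safety was confirmed would then claim more than the data can carry.

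**Working it through.** **Inputs.** Final rule (14.1.2): review if 7 or more of 30; any attributable grade 3 or higher toxicity counts. Interim rule (14.4): halt if 3 or more of 10; neurotoxicity only. Benchmark (14.4): about 5%, for late grade 3 or higher neurotoxicity under standard chemoradiation.

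**The plan's own figures.** 6/30 = 20.0% and 2/10 = 20.0%, as the plan states. The benchmark is rounded: 5% × 30 = 1.5 patients, whereas 2/30 = 6.7%. There is no error rate to reproduce for either safety rule.

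**Operating characteristics.** With independent patients and true rate p:

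- Final rule not crossed: P(X ≤ 6), X ~ Binomial(30, p).
- Interim halt: P(Y ≥ 3), Y ~ Binomial(10, p).
- Neither rule crossed: sum over a = 0, 1, 2 of P(Y = a) × P(Z ≤ 6 − a), Z ~ Binomial(20, p). This treats every counted event as neurotoxicity, so that both looks count the same events.

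At p = 20% the last sum is 0.1074 × 0.9133 + 0.2684 × 0.8042 + 0.3020 × 0.6296 = 0.098 + 0.216 + 0.190 = 0.504.

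| True rate | 6 or fewer of 30 | Interim halt (more than 2 of 10) | Neither rule crossed |
|---|---|---|---|
| 10% | 0.974 | 0.070 | 0.916 |
| 15% | 0.847 | 0.180 | 0.746 |
| 20% | 0.607 | 0.322 | 0.504 |
| 25% | 0.348 | 0.474 | 0.277 |
| 30% | 0.160 | 0.617 | 0.123 |

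The chance of not crossing the final rule falls below one half at a true rate of 22.0%; for both rules together, at 20.1%.

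**Precision (exact Clopper-Pearson limits, n = 30).**

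| Events | Two-sided 95% CI | One-sided 95% upper limit |
|---|---|---|
| 2 | 0.8% to 22.1% | 19.5% |
| 3 | 2.1% to 26.5% | 23.9% |
| 6 | 7.7% to 38.6% | 35.7% |

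On a one-sided 95% limit, only 2 or fewer events exclude 20%. On the upper end of the two-sided interval, 2 events do not (22.1%) and 1 event does (17.2%). The plan therefore has to say which limit it uses.

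**How often 2 or fewer of 30 would occur.** 0.411 at a true counted rate of 10%, 0.151 at 15% and 0.044 at 20%.

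**The case against.** The plan does not say in words that 6 or fewer events confirms safety. The count triggers review by the study team, and the interim crossing pauses accrual for committee review. Section 14.4 also has the radiation necrosis rate determined, and section 13 provides regular toxicity review. A trial of 30 cannot be precise, and simple triggers are reasonable at this stage. All of this stands, and it is why the counts should be kept as triggers. It does not support the word *confirmed* or the assertion that 30 patients suffice.

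Three stronger readings are tempting, and the documents do not support them.

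- *A regimen with four times the expected neurotoxicity passes more often than not.* The 5% refers to late neurotoxicity, while the final rule counts any attributable grade 3 or higher toxicity, for which the plan gives no expected rate. For a regimen with 20% neurotoxicity, 0.607 is an upper bound. If a further 2 percentage points of patients have only other counted toxicity, the final rule alone gives P(X ≤ 6) = 0.499 at 22%. With the interim look, the figure at 20% is already a coin flip. The multiple also depends on the rounding: against 2 of 30, 6 of 30 is three times.
- *A regimen at or above 20% will probably be reported as safe.* At 25% and 30% the final rule is not crossed with probability only 0.35 and 0.16.
- *Two or fewer of 30 should be the success criterion.* The plan uses 20% as a review threshold, not as a rate to be ruled out. A regimen with a true counted rate of 10% would meet such a criterion only 41% of the time. The 5% benchmark cannot be used to justify it. The temozolomide table in section 5.1 shows 80 of 288 (28%) with any grade 3 or higher reaction on standard concurrent treatment; these are not filtered for attribution to radiotherapy, but they show that 5% cannot be assumed for the wider endpoint.

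The remark in section 4.1 about incidence ("although the incidence may be slightly increased") describes risk; it is not a criterion and does not settle the matter either way.

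**Conclusion.** The concern holds as a point about what may be concluded. At a true counted rate equal to the plan's own 20% threshold, the final rule raises no question 61% of the time, and neither rule does 50% of the time. An observed 6 of 30 leaves rates up to 38.6% within the exact 95% interval. Staying under the trigger is therefore weak evidence of safety.

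Separately, the interim rule is a modest safeguard for its stated purpose. It halts accrual with probability 0.07, 0.18 and 0.32 at true neurotoxicity rates of 10%, 15% and 20%. Here the 5% figure concerns the same kind of event, although it is for late toxicity and the rule looks only to 6 months.

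The probabilities assume independent patients with a common event rate and all 30 evaluable at 6 months. The joint figures also assume that all counted events are neurotoxicity and that crossing the interim rule counts as not passing, although accrual may reopen after review. The interval for 6 of 30 needs neither of these last two assumptions. The defect lies in the stated conclusion and its missing justification; it does not show that the triggers themselves are wrong.

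**What to change.** 1. Keep more than 6 of 30 and more than 2 of 10 as review triggers, unchanged.
2. In 14.1.2, replace the statement that safety will be confirmed with an estimate of the counted grade 3 or higher rate and its exact 95% confidence interval.
3. Base the safety conclusion on that interval. Say that a rate of 20% is excluded only if the upper limit is below 20%, and name the limit in advance (for a one-sided 95% limit, 2 or fewer of 30). Otherwise report that 20% is not excluded, with the interval. Present this as a rule for wording the conclusion, not as a success criterion that the trial must meet.
4. In 14.4, print the operating characteristics of both rules across a range of true rates, as tabulated above.
5. Do not set the all-toxicity rule against the 5% neurotoxicity benchmark. If an expected rate is wanted for the wider endpoint, state one for that endpoint with its source.
6. In 14.5, tie the sentence on sufficient data to this precision, or delete it.

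The cost is wording in section 14, with no added patients and no change to treatment or triggers. The downside is that 3 to 6 events could no longer be described as confirming safety, and such a result is likely even for a regimen with a true rate well under 20%.
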